9.5 ALT or AST Elevations

A treatment-emergent ALT $\geq 3 \times$ ULN and/or AST $\geq 3 \times$ ULN is considered an AESI. Any participant with this laboratory result after atogepant was taken must have repeat testing within 48 to 72 hours to confirm the abnormality. For this repeat testing, the following laboratory tests must be performed: hematology and chemistry panels, INR, serum acetaminophen level, urine drugs of abuse screen, and blood alcohol level. A blood serology sample must be collected and sent to the central laboratory for further diagnostic testing at a later date, if needed. In addition, the investigator will perform a complete history and examination to evaluate the participant for possible liver disease.

All AESIs must be reported to Sponsor within 24 hours of the time the investigator becomes aware of the event using the abnormal liver function reporting form and the AE eCRF. All new

elements of history, physical examination, diagnostic testing results, and other relevant medical reports are to be reported for each AESI.

If an ALT or AST $\geq 3 \times$ ULN is confirmed, close medical follow-up is required:

For these participants, the following laboratory tests must be performed: anti-hepatitis A IgM, hepatitis B surface antigen, anti-hepatitis B core IgM, hepatitis C antibody, hepatitis C quantitative RNA by polymerase chain reaction, anti-hepatitis E IgM, anti-hepatitis E IgG, Cytomegalovirus IgM antibody and Epstein-Barr Virus IgM antibody. The participant must be followed clinically and further medical evaluation (for other causes of acute hepatic injury) should be done per the judgment of the investigator and in conjunction with Sponsor medical personnel. In general, the chemistry panel should be repeated 1 to 2 times per week to follow the course of ALT/AST elevation.

Atogepant must be discontinued if any of the following criteria are met:

- ALT or AST $\geq 3 \times$ ULN and the participant is symptomatic with the appearance of fatigue, nausea, vomiting, right upper quadrant pain or tenderness, fever, rash, or eosinophilia ($> 5\%$)
- ALT or AST $\geq 3 \times$ ULN and total bilirubin $> 2 \times$ ULN
- ALT or AST $\geq 3 \times$ ULN and INR > 1.5
- ALT or AST $\geq 5 \times$ ULN for more than 2 weeks
- ALT or AST $\geq 8 \times$ ULN

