The participant may be rechallenged with atogepant only after consultation with the Sponsor Medical Monitor. For participants who are not rechallenged, the participant should be discontinued from the study and complete an ET visit and an EOS Visit 4 weeks later. Participants should receive appropriate follow-up as per standard of care.

The investigator must contact the Sponsor Medical Monitor to discuss all cases of confirmed ALT/AST elevation $> 3 \times$ ULN. All ALT/AST elevations must be followed until ALT and AST return to $< 1.5 \times$ ULN and there is full clinical resolution.

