**Table 6-10 Safety Analysis Visit Definitions**

Analysis Phase	Analysis Visit (Derived)	Scheduled Study Visit (eCRF)	Window
Pretreatment	Baseline	Visit 1 for De Novo EM Participant only	Baseline from lead-in study for 3101-303-002 Completer Treatment Day $\leq 1$ for De Novo EM Participant
Open-label Treatment Period	Week 4	Visit 2	Treatment Day [1, 42] for 3101-303-002 Completer Treatment Day [2, 42] for De Novo EM Participant
	Week 8	Visit 3	Treatment Day [43,70]
	Week 12	Visit 4	Treatment Day [71,98]
	Week 16	Visit 5	Treatment Day [99,126]
	Week 20	Visit 6	Treatment Day [127,154]
	Week 24	Visit 7	Treatment Day [155,182]
	Week 28	Visit 8	Treatment Day [183,210]
	Week 32	Visit 9	Treatment Day [211,238]
	Week 36	Visit 10	Treatment Day [239,266]
	Week 40	Visit 11	Treatment Day [267,294]
	Week 44	Visit 12	Treatment Day [295,322]
	Week 48	Visit 13	Treatment Day [323,350]
	Week 52	Visit 14/ET	Treatment Day $\geq 351$ and within open-label treatment period
	End of treatment		Last available assessment during open-label treatment period
Safety Follow-up Period	Week 56 (Safety follow-up)	Visit 15	Treatment Day [the end of open-label treatment period +1, the last study visit]
	End of study		Last available assessment after treatment start date, i.e., occurs at final visit (expected Day 392) or ET

ET = early termination

Safety follow up visit will be presented in analysis tables for clinical laboratory values and vital signs.

End of Open label Treatment is defined as the last available assessment during open label treatment period. End of Open label Treatment results will be presented in analysis tables for clinical laboratory values, electrocardiograms and vital signs.

End of Study is defined as the last available assessment during the study, including open label and safety follow up period. End of Study results will be presented in analysis tables for safety parameters, including but not limited to clinical laboratory values, and vital signs.

For endpoints collected by visit, the last visit with a non-missing value will be used for analysis, if a participant has 2 or more visits within the same window.

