#### **6.4.4. Repeated or Unscheduled Assessments of Safety Parameters**

Baseline is defined as the last assessment made before the first dose of study treatment. If end-of-study assessments are repeated or if unscheduled visits occur, the last non-missing postbaseline assessment will be used as the end-of-study assessment for generating summary statistics. However, all postbaseline assessments will be used for PCS value determinations, and all assessments will be presented in the data listings.

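### The last-visit-in-window rule lets result-triggered ALT/AST retests replace the scheduled value in the by-visit laboratory statistics for Weeks 4 to 48 (minor; liver event counts are unaffected)

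*SAP*

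**What the plan says.** **Windows and selection rule.** SAP Table 6-10 assigns safety values to visits by treatment day. From Week 8 to Week 48 the windows are contiguous 28-day blocks around the visit day. Week 4 runs to Day 42. Week 52 starts at Day 351 and is limited to days "and within open-label treatment period". Where a window holds more than one visit, "the last visit with a non-missing value will be used for analysis, if a participant has 2 or more visits within the same window".

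**Tables that use it.** SAP 5.4.4.1 plans descriptive statistics of laboratory values and changes from baseline at each time point, including ALT and AST. SAP 5.1 lists the statistics: mean, SD, median, quartiles, minimum and maximum. SAP 5.5.1 repeats all safety analyses by cohort.

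**Retesting.** Under Protocol 9.5, a participant with ALT or AST of at least 3 x ULN on atogepant "must have repeat testing within 48 to 72 hours to confirm the abnormality". The repeat includes full hematology and chemistry panels. If the elevation is confirmed, in general "the chemistry panel should be repeated 1 to 2 times per week to follow the course of ALT/AST elevation". The section adds "All ALT/AST elevations must be followed until ALT and AST return to" below 1.5 x ULN, with full clinical resolution.

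**Unscheduled samples.** Protocol 8.6 places additional laboratory assessments under unscheduled visits, each with its own eCRF. SAP 6.4.4 gives an explicit summary-statistics rule for repeats and unscheduled visits only for the end-of-study assessment. It then says: "However, all postbaseline assessments will be used for PCS value determinations".

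**The concern.** Whether a second sample exists in a window depends on the first result. A participant with normal transaminases normally has one sample per window and keeps it. A participant at or above 3 x ULN has at least two, and the later one is kept. The row labelled with a scheduled week would then mix scheduled values from most participants with result-triggered follow-up values from those who had an elevation. Because the repeat is a full panel, their other chemistry values and their hematology values are replaced too.

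Safety is the primary objective, and an ALT or AST elevation of at least 3 x ULN is a named event of special interest. At stake is whether the by-visit means, SDs, maxima and changes from baseline describe the scheduled visit, and whether they agree with the event tables beside them.

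**Working it through.** The plan states no figure to reproduce here. The check has three parts.

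**1. Do the retests fall in the same window?** Inputs: visit days and the ±3-day allowance (Protocol Table 1), window limits (SAP Table 6-10), retest interval (Protocol 9.5).

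- For k = 1 to 12 (Weeks 4 to 48), the scheduled visit is on Day 28k ± 3 and the window ends on Day 28k + 14.
- Latest confirmatory repeat, counting 72 hours from the sample: 28k + 3 + 3 = 28k + 6, inside the window in all 12 cases. If the clock runs from receipt of the result, there are still (28k + 14) − (28k + 6) = 8 days to spare.
- Days left in the window after the scheduled visit: 14 − 3 = 11 to 14 + 3 = 17. After the repeat, 11 − 3 = 8 to 17 − 2 = 15 days remain, so roughly the first one to two weeks of follow-up samples share the window.
- Later samples fall in the next window, where the next scheduled visit would normally supersede them.
- Week 52: Visit 14 is on Day 364 to 367, so a repeat falls between Day 366 (364 + 2) and Day 370 (367 + 3). The window closes with the treatment period, so the repeat would normally go to follow-up. Visit 15 (Day 389 to 395) would normally be the last value there.

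**2. Does the rule reach unscheduled samples?** From Week 8 to Week 48, two on-time scheduled visits cannot share a window, because they are 28 days apart and sit near the middle of their windows. The rule then acts mainly on unscheduled or early-termination visits. In Week 4 it also resolves the Completers' Day 1 sample, because their window starts on Day 1. Nothing in the note limits it to scheduled visits.

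**3. How large is the shift?** The documents give no event rate, ULN or recovery time, so the values below are assumptions. Shift in the visit mean = (last value − scheduled value) / n for one participant. The mean change from baseline moves by the same amount.

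With ULN = 40 U/L:

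| Scheduled to last | n = 170 | n = 30 |
|---|---|---|
| 200 to 60 U/L (5 to 1.5 x ULN) | −140/170 = −0.82 U/L | −140/30 = −4.67 U/L |
| 120 to 60 U/L (3 to 1.5 x ULN) | −60/170 = −0.35 U/L | −60/30 = −2.0 U/L |
| 120 to 240 U/L (3 to 6 x ULN) | +120/170 = +0.71 U/L | +120/30 = +4.0 U/L |

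The SD and maximum are more sensitive. Suppose the other 29 De Novo participants have mean 20 and SD 8 U/L:

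- With 200 kept: SD = √[(28 × 64 + (29/30) × 180²)/29] = √(33,112/29) ≈ 33.8.
- With 60 kept: SD = √[(28 × 64 + (29/30) × 40²)/29] = √(3,338.7/29) ≈ 10.7.
- This participant's contribution to the maximum falls from 200 to 60.

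**The case against.** **No liver event is lost.** A reader might infer that the rule hides hepatic events. The documents do not support that. PCS counts and Table 6-4 need only one qualifying post-baseline value during the study. Potential Hy's law cases are summarised from first dose to end of study. Adjudicated cases are listed with their ALT and AST values, and all assessments are listed. No hepatic threshold table is defined by visit. This stands in full.

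**The direction is not fixed.** A reader might also infer a one-way bias toward normal. An unconfirmed elevation is lower on repeat, and a confirmed one is followed down below 1.5 x ULN, so downward is the expected direction. But a repeat can exceed the first value, and the last-value rule then raises the summary. This stands.

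**The premise is not explicit.** The SAP never says that a retest counts as a visit for Weeks 4 to 48, and Table 6-10 has a scheduled-visit column. This stands in part. Protocol 8.6 and SAP 6.4.4 both treat such samples as unscheduled visits, and the note does not exclude them. If the sponsor intended otherwise, the SAP still needs to say so.

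**Scope is limited.** Week 52 is normally spared. For a participant who discontinues, samples after the treatment period belong to follow-up. Extending the point to ECGs and vital signs is tempting because the same note covers them, but the documents specify no result-triggered post-baseline repeats for either, so no such bias is shown. These limits stand.

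**The effect is small.** There is no statistical hypothesis, one participant barely moves the median or quartiles, and the overall mean shifts by about 0.02 x ULN (3.5/170). This stands and sets the severity.

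**Conclusion.** The point holds as a minor defect in record selection. For Weeks 4 to 48, as the note is written, a sample taken because the scheduled ALT or AST was high can replace that value in the by-visit descriptive statistics, and only in participants with an elevation. The likely effect is to pull those statistics toward normal. A by-visit maximum could then omit the value that led to adjudication, although that value remains in the case-level and any-value outputs.

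The mean shift of about 0.8 U/L overall and 4.7 U/L in a cohort of 30 rests on one participant, an assumed ULN of 40 U/L and a fall from 200 to 60 U/L before the window closes. A milder elevation or slower recovery gives less; several events at one visit give more. The larger figure also requires the event to occur in the De Novo cohort. The conclusion assumes that unscheduled samples enter the windows by treatment day, which is the natural reading but is not stated.

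**What to change.** Add one sentence to the note under SAP Table 6-10. For by-visit descriptive summaries of laboratory parameters, use the scheduled-visit value. If two scheduled visits fall in one window, use the one closest to the target day. Use a repeat or unscheduled value only when the scheduled one is missing. State that all post-baseline values continue to feed the PCS, Table 6-4 and potential Hy's law outputs and the listings, as now.

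The closest-to-target clause also handles the Completers' Day 1 sample in the Week 4 window. The End of Treatment and End of Study rows are last-value summaries by definition and need no change.

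**Cost:** one SAP sentence and a change in record selection, with no new data. **Downside:** a later, higher unscheduled value would no longer appear in the by-visit table, but the any-value outputs still capture it. An early-termination sample that shares a window with a scheduled visit nearer the target day would leave that by-visit row, but it remains eligible for the End of Treatment row if taken within the treatment period.

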## 6.4.2. Derived Efficacy Data

### 6.4.2.1. Derivation of Efficacy Endpoints Based on eDiary Data

For analysis purposes, four weeks (28 days) will be considered as one month. On a daily basis during the 4-week baseline period and throughout the open-label treatment period, participants are to record eDiary information on the duration of headache, headache specific characteristics and symptoms, the pain severity, and use of any acute headache pain medication. Daily headache diary data consists of data from "today's diary" completed on that day and "yesterday's diary" completed on the following day. Participants are to report headache data in "today's diary" in the evening at any time from 19:00 to 23:59 and to complete "yesterday's diary" on the following day to add the remaining headache data of previous evening until midnight. In case participants miss "today's diary," they can report the whole-day headache data in "yesterday's diary" on the following day. In case participants miss "yesterday's diary," headache data from "today's diary" alone will be used as daily headache diary data. If both "today's diary" and "yesterday's diary" are missing on one day, the daily headache diary data will be treated as missing.

Daily headache diary data will be merged from "today's diary" and "yesterday's diary" as following and will be used to derive migraine day and headache day.

- Daily headache total duration: summation of headache durations from "today's diary" and "yesterday's diary"
- Daily headache pain severity: the worst pain severity from "today's diary" and "yesterday's diary"
- Daily headache characteristics and symptoms: present if present in one of "today's diary" and "yesterday's diary"
- Daily acute headache medication usage: combination of acute headache medications usage from "today's diary" and "yesterday's diary"

The date (COLLDAT) and time of the daily headache diary will be used for merging "today's diary" and "yesterday's diary" for 3101-303-002 rollover CM participants to align with the eDiary data derivation in 3101-303-002 study. The collection date (COLLDAT) is the date the daily headache diary is for, and collection time (COLLTIM) is triggered by the opening of the daily headache diary. Due to the eCOA vendor no longer collecting collection time in the EM cohort, the start date (STDAT) and time (STTIM) of the daily headache diary, which is the date and time when the daily headache diary is opened, will be used for merging "today's diary" and "yesterday's diary" for De Novo EM participants.

If a participant confirmed no headache for the Question 1 in eDiary, then the participant will not answer subsequent questions related to headache symptoms, duration, and acute headache medication use by design. Thus, the acute medication use for that diary ('today' or 'yesterday') will be treated as 'No' when deriving acute medication use day.

If a participant reported multiple records on the same day for one specific category ('Today' or 'Yesterday') and records are inconsistent, then the records for that eDiary category on the date with discrepancy will be excluded from endpoint derivation and thus excluded from the analyses. The corresponding records will be flagged in the analysis datasets.

If there are duplicate records of daily diary data for the same participant on the same day with the same type, the set of records with the last form access datetime will be used in the analysis.

The monthly migraine days is defined the total number of recorded migraine days in the eDiary divided by the total number of days with eDiary records during each monthly period and multiplied by 28. **For baseline, a minimum of 20 days' eDiary data during the 4-week baseline period is required for the migraine days to be evaluable.** For each postbaseline 4-week treatment period, a minimum of 14 days' eDiary data during that period is required for the migraine days to be evaluable. If a participant does not have at least 14 days of diary data for a monthly treatment period, the migraine days for that period will be considered as missing. Migraine days will be derived for each participant at baseline and for each postbaseline monthly treatment period (Weeks 1-4, 5-8, 9-12, 13-16, 17-20, 21-24, 25-28, 29-32, 33-36, 37-40, 41-44, 45-48, 49-52). The same method to derive monthly migraine days will be used to derive monthly headache days, monthly acute medication use days, monthly triptan use days, monthly cumulative headache hours, monthly moderate/severe headache days, and monthly severe headache days.

If a participant confirmed that acute medications were taken and entered medications in the eDiary, then the acute medication use day will be set to 'Yes.' If a participant reports 'Yes' to the intake of allowed medication(s) to treat an acute migraine but does not list any of them in the diary, then the acute medication use days will not be counted in this situation and vice versa.

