## **5.3. Efficacy Endpoint Analyses and Health Outcome Measures**

### **5.3.1. Definition of Endpoints**

Since the primary objective of this open-label extension study is to assess the safety and tolerability over 52 weeks of atogepant treatment, efficacy endpoints are not classified as primary, secondary, or additional.

Efficacy endpoints are listed below, and will be analyzed descriptively.

- Change from baseline in monthly migraine days at each monthly period (i.e., each consecutive 4-week period)
- Change from baseline in monthly headache days at each monthly period
- Change from baseline in monthly acute medication use days at each monthly period  $\geq 25\%$ ,  $\geq 30\%$ ,  $\geq 50\%$ ,  $\geq 75\%$ , and 100% improvement (decrease) in monthly migraine days at each monthly period
- Change from baseline in monthly triptan use days at each monthly period
- Change from baseline in monthly moderate/severe headache days at each monthly period
- Change from baseline in monthly severe headache days at each monthly period

- Change from baseline in monthly cumulative headache hours at each monthly period
- At least a 5-point improvement (decrease) from baseline in total HIT-6 score at each monthly period
- Change from baseline in the HIT-6 total score at each monthly period
- Rating of "much better" or "very much better" at Weeks 12, 24, 36, 48, and 52 assessed by the PGIC
- Change from baseline in percent work time missed, percent impairment while working, percent overall impairment, and percent activity impairment due to migraine at each monthly period as assessed by the WPAI:MIGRAINE
- Change from baseline in EQ-5D-5L descriptive system index score at each monthly period
- Change from baseline in the EQ-5D-5L VAS score at each monthly period
- Participants reporting "satisfied" or "extremely satisfied" with study medication for migraine prevention at each monthly period
- Change from baseline in monthly Performance of Daily Activities domain score of the AIM-D at each monthly period
- Change from baseline in monthly Physical Impairment domain score of the AIM-D at each monthly period
- Change from baseline in monthly AIM-D total score at each monthly period
- Change from baseline in monthly activity level at each monthly period
- Change from baseline in monthly activity limitation at each monthly period
- Change from baseline in MIDAS absenteeism score (Questions 1, 3, and 5) at Weeks 12, 24, 36, 48, and 52

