### **5.3.2. Main Analytical Approach**

Descriptive statistics will be provided by visit for all efficacy endpoints based on the mITT population using the observed case (OC) approach. No inferential statistical analyses will be performed for the efficacy endpoints except where noted above.

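### A post-baseline month with as few as 14 of 28 diary days and no recorded migraine counts as 100% improvement; among evaluable months this error can only raise the 100% responder rate

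*SAP*

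**What the plan says.** SAP 5.3.1 lists several responder thresholds, among them "and 100% improvement (decrease) in monthly migraine days at each monthly period"; protocol 7.2 also lists the 100% threshold.

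The derivation is in SAP 6.4.2.1. Recorded migraine days are "divided by the total number of days with eDiary records during each monthly period and multiplied by 28", and a month is 28 days. After baseline, a month is evaluable with 14 diary days; when someone "does not have at least 14 days of diary data for a monthly treatment period, the migraine days for that period will be considered" missing. The baseline minimum is higher, at 20 days of "eDiary data during the 4-week baseline period is required for the migraine days to be evaluable".

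A day counts as unrecorded only when the same-day and next-day entries both "are missing on one day, the daily headache diary data will be treated as missing". SAP 5.3.2 adds: "Descriptive statistics will be provided by visit for all efficacy endpoints based on the mITT population using the observed case (OC) approach".

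The SAP gives no separate derivation for the responder thresholds, no stricter diary minimum for the 100% threshold, and no sensitivity analysis on diary completeness.

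**The concern.** Proration works for a mean. If days are missing for reasons unrelated to migraine, the recorded fraction estimates the monthly fraction without bias. A claim of no migraine days at all is different. Zero recorded days prorate to zero however few days were recorded, so the derived value cannot separate a migraine-free month from one whose migraine days all fell on unrecorded days.

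The error has one direction. With correct entries, a truly migraine-free month always scores zero, whatever is missing. A month with true migraine days may also score zero.

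At stake is how the 100% responder rate is read. It is reported for 13 consecutive months, by cohort and overall, with no control arm. If diary completion differs between months or cohorts, part of any difference in this rate could reflect diary keeping rather than migraine.

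**Working it through.** The plan states no responder rate and no diary completion figure, so there is no figure of its own to reproduce.

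**Inputs from SAP 6.4.2.1:** month length 28 days; derived value = 28 × (recorded migraine days) / (recorded days); post-baseline minimum 14 recorded days.

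**Inputs assumed here:** which days are missing (at random), how many days are recorded, and the distribution of true monthly migraine days.

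**Step 1, the rule.** With 14 recorded days, 0 recorded migraine days give 28 × 0/14 = 0, a 100% responder. One recorded migraine day gives 28 × 1/14 = 2, not a 100% responder. A month is a 100% responder exactly when no migraine day is recorded.

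**Step 2, one month.** With k true migraine days and m of 28 days recorded at random, the probability that none is recorded is C(28−k, m)/C(28, m). At m = 14:
- k = 1: 14/28 = 50%
- k = 2: (14×13)/(28×27) = 182/756 = 24%
- k = 3: (14×13×12)/(28×27×26) = 2184/19656 = 11%

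| Recorded days | k = 1 | k = 2 | k = 3 |
|---|---|---|---|
| 14 | 50% | 24% | 11% |
| 20 | 29% | 7% | 2% |
| 26 | 7% | 0.3% | 0% |
| 28 | 0% | 0% | 0% |

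**Step 3, a cohort in which every month has the same number of recorded days.** The step 2 probability is averaged over a negative-binomial distribution of true monthly days, size parameter 1.2, truncated at 28. Case A has mean 3.5. Case B has mean 9 before truncation and 7.9 after it. Gains are in percentage points, taken before rounding the rates.

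| | True rate | Gain at 26 days | Gain at 24 | Gain at 20 | Gain at 14 |
|---|---|---|---|---|---|
| Case A | 19.4% | 1.28 | 2.72 | 6.24 | 13.99 |
| Case B | 8.0% | 0.62 | 1.35 | 3.18 | 7.61 |

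If every month sat at 14 days, 19.4% would read as 33.4% and 8.0% as 15.6%.

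**Step 4, mixed completion (assumed).**
- High (50% of months at 28 days, 40% at 26, 10% at 20). Case A: 0.4×1.28 + 0.1×6.24 = 1.1 points. Case B: 0.4×0.62 + 0.1×3.18 = 0.6 points.
- Moderate (30% at 28, 40% at 24, 20% at 20, 10% at 14). Case A: 0.4×2.72 + 0.2×6.24 + 0.1×13.99 = 3.7 points. Case B: 0.4×1.35 + 0.2×3.18 + 0.1×7.61 = 1.9 points.

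**Step 5, other endpoints.** Under a further assumed distribution (negative binomial, mean 6, size 1.5, truncated at 28) with 14 recorded days, the mean is unchanged (5.876 true, 5.876 derived). The share with at least 50% improvement moves either way: 49.7% becomes 54.1% with a baseline of 8 days, and 79.7% becomes 76.5% with a baseline of 18. Of the endpoints checked, only the 100% threshold shows a one-way error.

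**The case against.** A reader might infer that the reported 100% rate is biased upward overall, and that it will climb over 52 weeks as diary keeping declines. The documents support neither. The one-way argument covers only misclassification among evaluable months. The analysis uses observed cases, and months with fewer than 14 diary days drop out. If people without migraine stop filling in the diary, true 100% months are lost and the rate falls. Days missed because of migraine would enlarge the misclassification; days missed when well would shrink it. No completion figure or trend is given. This part of the objection stands in full.

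The large figures in step 3 need every participant to be exactly at the minimum. Several provisions make that unlikely: a missed day can be entered the next day (SAP 6.4.2.1), sites review the diary at each treatment visit from Visit 2 (protocol 8.4.2.2 and 8.4.2.3), and De Novo participants must complete at least 20 of 28 baseline days to enter (protocol 4.3.3). These reduce the number of unrecorded days but leave the rule as it is.

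The contrast between 20 days at baseline and 14 afterwards might be read as an error. It is not one: baseline completion is also an entry criterion for De Novo participants and the baseline value is the reference for every later change, so a different post-baseline minimum is a legitimate stated choice.

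Finally, SAP section 2 states no hypothesis, and efficacy endpoints are descriptive and unranked. Among the responder thresholds, only at least 50% improvement is named for a point estimate with a confidence interval (SAP 5.3.1). That limits the consequence. It also argues against making a subset with near-complete diaries the main result, since that would exchange misclassification for selection of unknown direction.

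**Conclusion.** The mechanism follows from the SAP's own rule and needs no assumption beyond correct diary entries: among evaluable months, incomplete diaries can only add 100% responders. The size is uncertain. Assuming randomly missing days and the negative-binomial distributions above, the addition is about 0.6 to 1.1 points with high completion and 1.9 to 3.7 with moderate completion; 8 to 14 points is an extreme that requires every month at 14 days. Misclassification mainly affects months with one to four true migraine days.

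The sign of the net error in the reported rate cannot be settled from the documents, because the effect of dropping months with fewer than 14 days is unknown. This is a minor point about interpreting one descriptive endpoint. It does not touch the safety objective.

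**What to change.** Keep the prespecified 14-day row as the main result. For the 100% threshold, add to the SAP:

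- A sensitivity row restricted, in numerator and denominator alike, to months with near-complete diaries, for example at least 26 of 28 recorded days. Removing only the incomplete months with zero recorded migraine days would bias the rate downward.
- In that sensitivity table, the other responder thresholds on the same denominator. Otherwise the 100% rate could exceed the rate for at least 75% improvement.
- By month and cohort, the distribution of recorded diary days and the number of 100% responders with fewer than 26 recorded days.

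The cost is a short SAP addition and a small table; no new data are needed. The added row rests on fewer months, from more diary-compliant participants, and at 26 days a month with one true migraine day still has a 7% chance of being scored as 100%. It should be read beside the main row, not in place of it.
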